## **4.2 Analysis methods**

### **4.2.1 Analysis of primary variable (OS)**

The analysis of OS will be done using stratified log-rank test stratified by PD-L1 status (positive versus negative), tumor location (OPC versus non-OPC, with a subsequent adjustment for HPV status in patients with OPC), and smoking history (>10 versus ≤10 pack-years) for generation of the p-value.

The stratification factors will be based on the values entered into IVRS at randomization even if it is subsequently discovered that these values were incorrect. Sensitivity analysis using the

correct values will be performed if more than 10% of the subjects were incorrectly categorized in the wrong strata.

The effect of MEDI4736 monotherapy versus SoC treatment in the relevant analysis populations (Table 12) will be estimated by the HR together with its corresponding 95% CI. The hazard ratio (HR) of OS, along with its 95% confidence interval using the same strata information as above will be estimated using a stratified Cox proportional hazards model with treatment as the only covariate (with ties= Efron and any stratification variables included in the strata statement) and the CI calculated using a profile likelihood approach.

Kaplan-Meier plots of OS will be presented by treatment arm. Summaries of the number and percentage of patients who have died, those still in survival follow-up, those lost to follow-up, and those who have withdrawn consent will be provided along with the median OS for each treatment.

An analysis of OS will again be performed to compare MEDI4736 + tremelimumab combination therapy versus SoC and MEDI4736 + tremelimumab combination therapy versus MEDI4736 monotherapy for the analysis populations described in Table 12.

**Impact of switching treatment post study treatment discontinuation to immunotherapies (or other potentially active investigational agents) on OS analyses**

CCI  
[Redacted text block]

[Redacted text block]

[Redacted text block]

The following treatment comparisons will be performed, based on the primary analysis model:

- PD-L1 TC/IC high subgroup – MEDI4736 monotherapy versus SoC
- All-comers - MEDI4736 monotherapy versus SoC
- All-comers – MEDI4736 + tremelimumab combination therapy versus SoC

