3.5 Methods for assigning treatment arms

Patients must not be randomized unless all eligibility criteria have been met.

At baseline, patients who satisfy all the entry criteria will be centrally assigned to study drug by the IVRS/IWRS, according to the randomization scheme generated by the Biostatistics Group, AstraZeneca, or delegate.

Patients enrolled in the study will be randomized (2:1:1) to treatment with MEDI4736 + tremelimumab combination therapy, MEDI4736 monotherapy, or SoC (cetuximab, a platinum [carboplatin or cisplatin based on Investigator's choice], and 5FU). Patients will be stratified by PD-L1 status (positive or negative, based on the analytically validated VENTANA/MedImmune assay), tumor location (OPC or non-OPC), and smoking history (>10 vs ≤10 pack-years). Patients with OPC will be further stratified by HPV status.

The actual treatment given to patients will be determined by the randomization scheme in the IVRS/IWRS. The randomization scheme will be produced by a computer software program that incorporates a standard procedure for generating randomization numbers. One randomization list will be produced for each of the randomization strata. A blocked randomization will be generated, and all centers will use the same list in order to minimize any imbalance in the number of patients assigned to each treatment arm.

Patients will be identified to the Centralized Randomization Center per country regulations. Randomization codes will be assigned strictly sequentially, within each stratum, as patients become eligible for randomization.

If a patient discontinues participation in the study, then his/her enrollment/randomization code cannot be reused.

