#### **MEDI4736 Monotherapy versus SoC in the ctDNA TMB high ( $\geq 16$ mut/Mb) subgroup (OS)**

Assuming approximately 16% of patients are in the ctDNA TMB high ( $\geq 16$  mut/Mb) subgroup and assuming the true OS HR is 0.40, the trial will have approximately 82% power to demonstrate statistical significance at the 5% level (using a 2-sided test) for the comparison of MEDI4736 monotherapy versus SoC in the ctDNA TMB high ( $\geq 16$  mut/Mb) subgroup, with approximately 48 events.

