#### **MEDI4736 + tremelimumab combination therapy versus SoC in the ctDNA TMB high ( $\geq 16$ mut/Mb) subgroup (OS)**

Assuming the true OS HR is 0.40, the trial will have approximately 92% power to demonstrate statistical significance at the 5% level (using a 2-sided test) for the comparison of MEDI4736 + tremelimumab combination therapy versus SoC in the ctDNA TMB high ( $\geq 16$  mut/Mb) subgroup, with approximately 68 events.

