#### 4.1 General principles

IVRS based stratification factors will be used for the analysis of primary objectives as well as the analyses for other secondary objectives namely; PFS, ORR, PFS2, TFST, TSST, Time to

deterioration of EORTC QLQ-C30 and EORTC QLQ-H&N35, improvement rate of EORTC QLQ-C30 and EORTC QLQ-H&N35.

The subgroup analyses for the stratification factors as well as all other factors will be based on values recorded on the CRF. If there is >10% discordance in stratification factors as recorded in IVRS versus the Case Report Form (CRF), then a sensitivity analysis of the primary objectives, will be performed using CRF based stratification factors. For this sensitivity analysis if there are missing baseline covariate values, patients will be retained in the analysis by including the missing data as another stratification level.

Other general principles that will be followed throughout the study include the following:

- Descriptive statistics will be used for all variables, as appropriate, and will be presented by treatment group. Continuous variables will be summarized by the number of observations, mean, standard deviation, median, minimum, and maximum. Categorical variables will be summarized by frequency counts and percentages for each category.
- Unless otherwise stated, percentages will be calculated out of the population total for the corresponding treatment arm.
- For continuous data the mean and median will be rounded to 1 additional decimal place compared to the original data. The standard deviation will be rounded to 2 additional decimal places compared to the original data. Minimum and maximum will be displayed with the same accuracy as the original data.
- For categorical data, percentages will be rounded to 1 decimal place.
- Results of all statistical analysis will be presented using a 95% confidence interval (CI) and 2-sided p-value, unless otherwise stated.
- All models will include 3 treatment groups and any pairwise comparisons will then be extracted.
- SAS® version 9.4 or higher will be used for all analyses.
- Palliative radiation will not be considered as a subsequent therapy.

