**Table 12 Pre-planned statistical and sensitivity analyses to be conducted**

Endpoints Analyzed	Notes
OS	Stratified log-rank tests and Cox proportional method for: Primary objective 
 
- MEDI4736 monotherapy versus SoC in the PD-L1 TC/IC high subgroup (stratified by PD-L1 status, tumor location, and smoking history)
 
 Secondary objectives 
 
- MEDI4736 monotherapy versus SoC in the low risk of EM subgroup, ctDNA TMB high (<math>\geq 16</math> mut/Mb) subgroup and all-comers; (stratified by PD-L1 status, tumor location, and smoking history)
 
- MEDI4736 + tremelimumab combination therapy versus SoC in the PD-L1 TC/IC high subgroup, low risk of EM subgroup, ctDNA TMB high (<math>\geq 16</math> mut/Mb) subgroup and all-comers (stratified by PD-L1 status, tumor location, and smoking history)
 
- MEDI4736 + tremelimumab combination therapy versus MEDI4736 monotherapy in the PD-L1 TC/IC high subgroup, low risk of EM subgroup, ctDNA TMB high (<math>\geq 16</math> mut/Mb) subgroup and all-comers; (stratified by PD-L1 status, tumor location and smoking history)
 
 Sensitivity analysis: 
 
- Sensitivity analysis using the stratified Max-combo test
 

Endpoints Analyzed	Notes

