### **Effect of covariates on the HR estimate (Cox Proportional Hazards model)**

As a sensitivity analysis, an unstratified Cox-proportional hazards modeling will be employed to assess the effect of covariates on the HR estimate for the primary analysis, i.e., the MODEL statement will include the treatment group variable and also the stratification factors (PD-L1 Status, smoking status and tumor location) as main effects. Hazard ratio with associated 95% CI will be based the profile likelihood approach.

This model will be done to ensure that any output from the Cox modeling is likely to be consistent with the results of the stratified log-rank test.

Moreover, another sensitivity analysis will be performed to evaluate the treatment effect, adjusted for pre-specified baseline prognostic factors. This analysis will be performed for the PD-L1 TC/IC high subgroup, low risk of EM subgroup, ctDNA TMB high ( $\geq 16$  mut/Mb) subgroup and all-comers. For this analysis, a stratified Cox model adjusted for the following covariates will be used. The covariates are:

- Sex at randomization (Male, Female)
- Age at randomization (<65,  $\geq 65 < 75$ ,  $\geq 75$  years of age)
- Race (Asian, non-Asian)
- WHO/ECOG performance status (0,  $\geq 1$ )
- Primary Tumor location/HPV (OPC/Positive, OPC/Negative, non-OPC/Any HPV)

- Extent of Disease (only locoregionally recurrent, metastatic with or without locoregional recurrence)

The Hazard ratio with two-sided 95% confidence interval will be based on profile likelihood approach.

The two models described above will include the effect regardless of whether the inclusion of effect significantly improves the fit of the model providing there is enough data to make them meaningful.

Interactions between treatment and the stratification factors will also be tested to rule out any qualitative interaction using the approach of [Gail and Simon 1985](#).

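### SAP 1.3 gives two conflicting powers for each TMB-high OS test (82% or 88%; 92% or 96%), and neither is shown to be the power of the stratified log-rank test planned

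*SAP*

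**What the plan says.** **Power.** SAP 1.3 has a short paragraph for each test in the hierarchy and then collects the figures in Table 5. For TMB-high monotherapy versus SoC (HR 0.40, about 48 deaths, two-sided 5%) the paragraph says "the trial will have approximately 82% power to demonstrate statistical significance"; Table 5 prints 88% for 30:30 patients, HR 0.40 and 48 deaths, with critical HR 0.56. For TMB-high combination versus SoC (HR 0.40, about 68 deaths) the paragraph says "the trial will have approximately 92% power to demonstrate statistical significance"; Table 5 prints 96% for 60:30 patients, HR 0.40 and 68 deaths, with critical HR 0.62. The table note exempts TMB-high from the 3-month delay assumed for the other tests.

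**Test.** SAP 4.2.1: "The analysis of OS will be done using stratified log-rank test stratified by PD-L1 status (positive versus negative), tumor location", then "with a subsequent adjustment for HPV status in patients with OPC", then smoking history. SAP Table 12 applies this to the TMB-high monotherapy comparison: "subgroup and all-comers; (stratified by PD-L1 status, tumor location, and smoking history". The combination comparison carries the same list. At randomisation, Protocol 3.5 says: "Patients with OPC will be further stratified by HPV status". SAP 4.1 adds: "All models will include 3 treatment groups and any pairwise comparisons will then be extracted".

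**Place in the hierarchy.** SAP section 4 puts the two TMB-high tests third and fourth of six, each at two-sided 5%, stopping at the first failure. Both all-comers tests come after them.

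**The concern.** The same inputs cannot give two powers. For the other four tests in the hierarchy the SAP 1.3 text and Table 5 agree (90%, 81%, 91% and 97%), so the conflict is confined to the TMB-high rows. The reader cannot tell which figure was relied on when these tests were placed ahead of the all-comers tests.

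There is a second question. An event-count formula gives the power of an unstratified comparison. The analysis is stratified, and with 48 deaths over 8 or 12 strata there are on average 6 or 4 deaths per stratum (48/8, 48/12). A death that occurs when only one arm is still at risk in its stratum contributes nothing to the log-rank statistic, so the formula may overstate what the planned test can do.

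At stake is how likely the hierarchy is to reach the all-comers tests. Type I error is not at stake.

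**Working it through.** **1. Inputs (SAP 1.3 and Table 5).** HR 0.40, no delay, two-sided 5% (z = 1.960). Patients: 16% of 190 is about 30 per arm for monotherapy and SoC; 16% of 380 is about 60 for the combination. Deaths: 48 of 60 (80%) and 68 of 90 (76%). The landmarks agree with the HR: 0.12^0.40 = 0.43, the 43% versus 12% in Table 5.

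**2. Expected deaths by arm.** Let s be SoC survival at the cut-off, treated as one common follow-up time; survival on treatment is then s^0.40.
- Monotherapy: 30(1 − s) + 30(1 − s^0.40) = 48 gives s ≈ 0.065, so about 28 SoC and 20 monotherapy deaths.
- Combination: 30(1 − s) + 60(1 − s^0.40) = 68 gives s ≈ 0.065, so about 28 SoC and 40 combination deaths.

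Allowing for 17 months of uniform accrual gives 20.1:27.9 and 40.1:27.9, practically the same.

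**3. Reproducing Table 5.** SE of log HR = √(1/d1 + 1/d2); power = Φ(|ln 0.40|/SE − 1.960); critical HR = exp(−1.960 × SE); |ln 0.40| = 0.916.
- Monotherapy: SE = √(1/20 + 1/28) = 0.293; power = Φ(3.130 − 1.960) = Φ(1.170) = 87.9%; critical HR 0.56.
- Combination: SE = √(1/40 + 1/28) = 0.246; power = Φ(3.719 − 1.960) = Φ(1.759) = 96.1%; critical HR 0.62.

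All four values match Table 5. The formula uses no strata.

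**4. Trying to reproduce the text.** With D deaths and arm shares p and q, the variance is 1/(D·p·q).
- 82% needs SE = 0.916/(1.960 + 0.915) = 0.319, so D = 1/(0.319² × 20/48 × 28/48) ≈ 40, not 48.
- 92% needs SE = 0.916/(1.960 + 1.405) = 0.272, so D = 1/(0.272² × 40/68 × 28/68) ≈ 56, not 68.

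Other standard formulas do not recover them. For monotherapy, Schoenfeld gives 88.8%, Freedman 84.4%, and Schoenfeld at one-sided 5% 93.7%. For the combination, Schoenfeld gives 94.5% at 2:1.

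**5. Power of the planned test.** The documents do not give stratum sizes or prognostic strength, so these are simulations under assumptions. Set A: SoC median 10.1 months and 12% at 24 months; HR 0.40 without delay; OPC 20-50%, HPV-positive 20-50% of OPC, more than 10 pack-years 50-90%, PD-L1 positive (25% tumor-cell cut-off) 20-50%; strata not, moderately or strongly prognostic; 36 scenarios per test. Set B: 30:30 with 48 deaths and 60:30 with 68, strata equal or skewed (35% PD-L1 positive, 35% OPC, 40% of OPC HPV-positive, 70% above 10 pack-years).

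| Test | Set A | Set B |
|---|---|---|
| Mono, two-arm risk sets, 12 strata | 72-84% | 71-76% |
| Mono, two-arm, 8 strata | 74-84% | 77-79% |
| Mono, three-arm, 12 or 8 strata | 78-85% | 80-83% |
| Mono, unstratified | 79-88% | 88% |
| Combo, two-arm, 12 or 8 strata | 89-94% | 89-92% |
| Combo, three-arm, 12 or 8 strata | 84-89% | not run |
| Combo, unstratified | 91-96% | 95-96% |

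The stratified monotherapy test therefore has roughly 71-85%. Against the unstratified test in the same scenario, the two-arm 12-stratum version loses 2-15 points in set A, least when the strata are strongly prognostic, and 13-18 points in set B (88.4% to 75.7%, 88.5% to 70.8%). Rejection under the null stayed between 3.9% and 6.0% throughout.

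**The case against.** Three objections deserve weight.

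**Sizing by an unstratified formula is common practice.** The same method reproduces the critical HRs of the other four Table 5 rows, so on this score TMB-high is no different from the rest. That stands as a matter of convention. But these are the smallest tests in the hierarchy, where the approximation is weakest, and the convention does not explain why the text and the table disagree.

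**The test itself is adequately specified.** A reader might infer that the role of HPV is undefined. SAP 4.2.1 puts HPV inside the stratification clause, then fits a Cox model on the same strata with treatment as the only covariate and the stratification variables in the strata statement. With Protocol 3.5, this points to HPV as strata within OPC, and the shorter list in Table 12 can be read as shorthand. Protocol Table 15 names no factors for the TMB-high rows, but Protocol 8.5.1.1 supplies them. The three-group sentence in SAP 4.1 speaks of models, so a two-arm log-rank is the ordinary reading. The covariate "Primary Tumor location/HPV (OPC/Positive, OPC/Negative, non-OPC/Any HPV" in the supportive adjusted Cox model would be constant within such strata, apart from IVRS/CRF discordance; it then drops out and leaves the treatment HR alone. These are matters of wording.

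**The lack of a sparse-stratum rule is a choice.** The stratified log-rank handles one-arm risk sets by construction. The gain from pooling in the simulations is between 0 and 13 points depending on the reading, and rests on assumed stratum sizes and on a threshold and dropping order that nobody has fixed. That stands in full.

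**Conclusion.** The contradiction holds and needs no assumptions: at identical inputs SAP 1.3 states 82% and 88% for monotherapy, and 92% and 96% for the combination. Table 5 is internally coherent as an unstratified calculation; the text figures are not reproduced by any formula tried.

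That the planned stratified test has lower power than 88% for monotherapy (roughly 71-85%) is a conditional result. It rests on assumed stratum sizes and prognostic effects and on the risk-set reading. It shows that 88% has not been established for this test; it does not establish a replacement value.

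Three stronger readings are tempting and are not supported:
- That 82% and 92% are the stratified powers. They lie inside or near the simulated stratified ranges, but nothing in the SAP says they allow for stratification.
- That the absence of a pooling rule is an error in the plan. It is a trade-off, with no type I error problem behind it.
- That the trial's main conclusion is exposed. SAP section 4 judges success on the PD-L1 TC/IC high test alone, the analysis is triggered by about 147 deaths in that subgroup, and the TMB-high tests are reached only after two prior rejections.

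The correction is worth making because it is cheap and the figures describe two tests that stand ahead of both all-comers tests.

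**What to change.** **Main change.** In SAP 1.3, make the two TMB-high paragraphs agree with Table 5, and restate both powers for the stratified log-rank test actually planned, giving the assumed stratum sizes, prognostic effects and risk-set convention. If the unstratified figures stay in Table 5, label them as such.

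**Minor clarifications.** In SAP 4.2.1, say that HPV status forms strata within OPC, as at randomisation, and say whether each pairwise log-rank test uses two-arm or three-arm risk sets. The second is worth a sentence: in set A the risk-set choice alone moves the combination test by about 5 points, and in set B two-arm and three-arm versions gave different significance verdicts in about 9-15% of simulated monotherapy trials.

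**Optional.** A pooling rule for sparse strata in the TMB-high tests, fixed before database lock, could be added if the sponsor judges the power gain worth losing adjustment for a dropped factor.

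**Cost.** SAP wording and a few restated figures. Enrolment, event target, timing and the primary test do not change.

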### **Sensitivity Analysis for OS variable**

A sensitivity analysis for OS will examine the censoring patterns to rule out attrition bias with regards to the primary treatment comparison. This analysis will be supported by Kaplan-Meier plot of time to censoring where the censoring indicator of OS is reversed.

In addition, to support OS analyses, duration of follow-up will be summarized using medians:

- In censored patients who are alive at data cut-off only: Time from randomization to date of censoring (date last known to be alive) by treatment arm.
- In all patients: Time from randomization to the date of death (i.e. overall survival) or to the date of censoring for censored patients regardless of treatment arm.

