### 1.3 Number of subjects

The sample size for this study was selected to be consistent with the research hypothesis as described in Section 8.5 of the Clinical Study Protocol (CSP).

The study will enroll approximately 1016 patients in order to randomize 760 eligible patients in a 2:1:1 ratio (380:190:190 patients) to MEDI4736 + tremelimumab combination therapy, MEDI4736 monotherapy, or SoC respectively.

The study was originally sized to characterize the OS benefit of MEDI4736 + tremelimumab combination therapy versus SoC in all-comers (i.e., regardless of PD-L1 tumor expression status) and in PD-L1 TC/IC subgroup population. The sizing assumes a 3-month delay in separation of the OS curves between each arm, hence the use of average HRs.

With amendment 11 (CSP version 12) the primary objective was changed to characterize the OS benefit of MEDI4736 monotherapy versus SoC in the PD-L1 TC/IC high subgroup. Due to this change the primary analysis of OS will be performed when approximately 147 death events have occurred in approximately 172 patients (85% maturity) across the MEDI4736 monotherapy and SoC treatment groups in the PD-L1 TC/IC high subgroup population. The number of patients (172) assumes that 45% of patients randomized are within this subgroup. No interim efficacy analyses will be performed in this study.

If superiority over SoC is found, a hierarchical multiple testing procedure (MTP) will be employed to strongly control for the overall type I error at the 5% alpha level (two-sided), as shown in Section 4, Figure 4.

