### 3.2.1 Primary endpoint (OS)

OS is defined as the time from the date of randomization until death due to any cause (i.e., date of death or censoring – date of randomization + 1). Any patient not known to have died at the time of analysis will be censored based on the last recorded date on which the patient was known to be alive (SUR\_DAT, recorded within the SURVIVE module of the eCRF).

Note: Survival calls will be made following the date of data cut-off for the analysis (these contacts should generally occur within 7 days of the data cut-off). If patients are confirmed to be alive or if the death date is post the data cut-off date, these patients will be censored at the date of data cut-off. Death dates may be found by checking publicly available death registries (as applicable under local laws).

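### The all-patients follow-up summary in SAP 4.2.1 restates pooled median survival; the median of the reversed-censoring curve already planned should be reported instead

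*SAP*

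**What the plan says.** Three statements in SAP 4.2.1, under Sensitivity Analysis for OS variable, bear on this.

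- The attrition check for the primary comparison is "supported by Kaplan-Meier plot of time to censoring where the censoring indicator of OS is reversed". No median is taken from this curve, and it is not named as the follow-up estimate. Protocol 8.5.1.1 plans the same plot and does not define a duration of follow-up.
- To support OS, "duration of follow-up will be summarized using medians". The first summary, by treatment arm, is "In censored patients who are alive at data cut-off only: Time from randomization to date of censoring".
- The second summary, for all patients, is "Time from randomization to the date of death (i.e. overall survival) or to the date of censoring for censored patients regardless of treatment arm".

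SAP 3.2.1 adds that, for patients confirmed alive after the cut-off or known to have died after it, "these patients will be censored at the date of data cut-off". SAP 1.3 times the analysis for when "approximately 147 death events have occurred in approximately 172 patients (85% maturity") in the PD-L1 TC/IC high subgroup, monotherapy and SoC arms.

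**The concern.** A follow-up figure should tell the reader how long patients were, or could have been, under observation, so that late parts of the survival curve can be judged. OS18 and OS24 are secondary outcomes here, so that information has a use. A statistic in which death ends the clock does not supply it once most patients have died. It lengthens when survival improves and shortens when survival worsens, whatever the calendar length of observation. At this trial's planned maturity the all-patients bullet would repeat a quantity that SAP 4.2.1 already reports by arm (median OS), with the arms merged and under the name follow-up.

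**Working it through.** **The plan's own figures.** Maturity: 147/172 = 85.5%, 336/380 = 88.4% and 495/570 = 86.8%, against 85%, 88% and 87% in SAP Table 5. Timing: 17 + 23.6 = 40.6 months, as stated. Power for 147 deaths at HR 0.59: |ln 0.59| × √147/2 − 1.96 = 3.20 − 1.96 = 1.24, which gives 89.2% against about 90%.

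**Inputs.** SoC median OS is 10.1 months and 24-month OS 12%. Monotherapy 24-month OS is 30% (PD-L1 high) or 24% (all-comers); the combination is 24% (all-comers). The curves separate after 3 months (SAP 1.3 and Table 5). My assumptions: uniform accrual and, at first, no loss to follow-up.

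**Step 1, without a survival model.** Patients alive are censored at cut-off, so censoring times run from 23.6 to 40.6 months. Pooled 24-month survival is (30 + 12)/2 = 21% for PD-L1 high, (24 + 12)/2 = 18% for all-comers monotherapy plus SoC, and 0.75 × 24 + 0.25 × 12 = 21% for the three arms. Half the patients have therefore died well before anyone is censored. The median of the smaller of death time and censoring time is then exactly the pooled median OS.

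**Step 2, its size.** Fit a Weibull SoC curve through the two stated points:

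- shape k = ln[ln(1/0.12)/ln 2]/ln(24/10.1) = 1.29, which gives S(3) = 0.866
- post-delay HR for PD-L1 high = ln(0.30/0.866)/ln(0.12/0.866) = 0.54
- at 12.1 months, SoC survival is 0.416 and monotherapy 0.584, with mean 0.50

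The pooled median is thus 12.1 months (10.1 for SoC, about 15.1 for monotherapy). Other curve shapes and populations, in months:

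| Population | Weibull | Piecewise exponential | Exponential |
|---|---|---|---|
| PD-L1 high, mono + SoC | 12.1 | 11.8 | 11.5 |
| All-comers, mono + SoC | 11.5 | 11.2 | 10.7 |
| All-comers, three arms | 12.3 | 11.9 | 11.0 |

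The plain exponential is only a check: it gives 0.5^(24/10.1) = 19% at 24 months, not 12%.

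**Step 3, reversed censoring.** With deaths treated as censored, the median of a censoring time uniform on 23.6 to 40.6 is (23.6 + 40.6)/2 = 32.1 months.

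**Step 4, the censored-patients bullet.** It covers 172 − 147 = 25 patients in the primary population. Later recruits are over-represented among those still alive, so its median is 29.1 to 30.2 months across the same nine cases, somewhat below 32.1.

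**Step 5, simulation** (1,000 trials of 172 PD-L1 high patients, Weibull). All-patients median 12.1 months (95% range 10.1 to 14.3), reversed-censoring median 32.2, censored-only median 29.6. The documents give no loss rate. At an assumed 5% and 10%, the all-patients median is 11.9 and 11.6 months and the reversed-censoring median 31.8 and 31.4.

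**The case against.** The best defence is that the SAP does not hide what it does. The bullet itself says that for patients who die the quantity is overall survival, and it stands beside a by-arm median in survivors that comes close to 32 months. On that view the bullet is simply observed time on study, and the name is convention. The transparency stands. The name does not: the list is introduced as duration of follow-up, and the only entry covering all patients does not measure it.

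Three stronger readings are tempting, and the documents do not support them.

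- *The trial's reported follow-up would be wrong by a factor of about 2.6 (32.1/12.1 = 2.65; 32.1/12.3 = 2.61).* That compares two different quantities and ignores the by-arm survivor median of about 29 to 30 months.
- *Pooling hides differences between arms in attrition.* The attrition check is the reversed plot for the primary comparison. SAP 4.2.1 also tabulates deaths, patients still followed, losses and withdrawals, and the survivor median is by arm.
- *The analysis would look immature.* Maturity is defined by deaths, and the number and percentage who died are reported.

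**Conclusion.** The point holds as a minor reporting correction. Barring appreciable early loss to follow-up, the all-patients median will equal the pooled median OS: about 11 to 12 months (10.7 to 12.3 across the curve shapes and populations tried). That result needs only the 23.6-month minimum follow-up and the stated 24-month survival rates. The survivor bullet compensates in part, but it selects on survival and uses about 25 of 172 patients.

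The 32 months is a planning value, not the follow-up that the trial will achieve. It assumes uniform accrual over 17 months, which the documents do not state, and cut-off at 40.6 months. Cut-off is event-driven, and the protocol synopsis spans Q4 2015 to Q1 2021, longer than 40.6 months. A later cut-off would lengthen the reversed-censoring median and leave the all-patients median where it is. Nothing here touches the log-rank test, the HR, alpha, power or the success criterion.

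**What to change.** In SAP 4.2.1:

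- Report the median with 95% CI from the planned reversed-censoring Kaplan-Meier curve as the duration of follow-up, by arm and overall, for the PD-L1 TC/IC high subgroup and all-comers.
- Keep the survivor bullet as descriptive support.
- Drop the all-patients bullet, or relabel it as observed time on study.

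The CI is needed because the by-arm estimates in the primary population will rest on few patients: at 24 months about 0.12 × 86 = 10 SoC and 0.30 × 86 = 26 monotherapy patients are expected alive. The cost is about one SAP sentence and one added statistic on a curve already planned. No protocol amendment is needed, since Protocol 8.5.1.1 contains the plot and does not define follow-up duration.
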